8.2 STUDY ENROLLMENT

The number of subjects to be enrolled in the study is up to 20. This sample size is estimated to be sufficient to yield acceptable, first-in-man, safety and effectiveness data for initial analysis and to support future regulatory submissions. It is anticipated that up to ten (10) centers inside the United States will be needed to enroll this study in a timely fashion. Each investigational site will be expected to enroll at least two (2) and up to eight (8) subjects.

8.3 INVESTIGATOR QUALIFICATION AND TRAINING

The MobiusHD system should only be used by interventionists with expertise in the navigation of catheter systems and stenting procedures. Qualified potential Investigators for this clinical trial will have successfully placed carotid stents in at least 10 patients in the 12 months prior to Site Initiation and 100 carotid stents during their careers.

Qualified study centers will be expected to work in research teams that include the appropriate specialties for the proper conduct of the study (e.g., interventional cardiologist(s) or neurointerventionalist(s) experienced in carotid stenting, internists, and study coordinator(s)). Qualified interventionists will have successfully performed carotid stenting in at least 10 patients in the last calendar year and 100 patients in their careers.

All Investigators and those to whom the Investigator delegates study responsibilities (see Investigator Agreement), will be trained on the Protocol by a representative of the Sponsor. Interventional Investigators using the investigational device will be trained on the Instructions For Use of the MobiusHD system. Additional training such as preparation and table-top deployment of a demonstration device, animal lab, and/or case support will be offered by Sponsor, as appropriate, to meet the needs of the site Investigators. In addition, training on topics such as Medical Imaging Guidelines ("Core Lab", Appendix I), internet-based CRF (iCRF) data entry procedures, and investigational device inventory management will be conducted at Investigator meetings and during site visits. All training completed will be appropriately documented. Research staff responsible for assessing neurological status using the NIHSS must be certified in the proper administration of this assessment tool. Training and Certification on administration of the NIHSS, if such documentation is not already available, can be obtained by taking a web-based accredited course such as: <http://nihss-english.trainingcampus.net/uas/modules/trees/windex.aspx>

8.4 SELECTION AND SCREENING OF SUBJECTS

Prior to subject participation in this study, the study team must obtain written IRB/EC approval for the Protocol and the ICF. The study population for this clinical trial will be comprised of adult patients who have been diagnosed with stage 2 resistant hypertension. In addition, these patients must satisfy the inclusion and exclusion criteria. The trial will prospectively enroll up to 20 subjects. Patients presenting with stage 2 resistant hypertension must be on a minimum of three (3) anti-hypertensive medications. Clinical site personnel will review the patient's medical history for eligibility. Potential candidates will be fully informed by a member of the research team as to the purpose of the study and the nature of the implantation procedure. The implantation procedure will be described and its potential risks and benefits will be explained in detail. Patients who voluntarily agree to participate in the trial will be asked to sign and date the written Informed Consent Form (ICF). If approved by the reviewing IRB/EC, subjects may indicate verbal, witnessed consent with the signature of a patient representative not associated with the study team if cognition is intact but the subject is unable to sign (e.g., the subject has inhibited hand function or visual disturbance).

The approved ICF must be signed for study enrollment prior to performing study related assessments. A copy of the signed and dated ICF should be provided to the subject. Subjects must be informed that they may withdraw from the study at any time, and for any reason, and will continue to receive therapy as indicated by their physician. Internet-based Case Report Forms must be completed for each subject who consents to study participation.

8.5 BASELINE ASSESSMENT: VISIT 1 (DAY 0-14) – ASSESSED DAY 14

The following information will be assessed and the documentation will be maintained as source records at the study site:

- Medical history;
- Office cuff blood pressure (Note: Office cuff BP recordings must be performed as detailed in Appendix IV);
- Check for orthostatic blood pressure and orthostatic pulse assessments;
- Daily patient diary assessments of blood pressure and medication compliance;
- Assessment for renal artery stenosis. If duplex, renal MRA, renal angiography or renal CTA has been performed in the 12 months preceding screening, and in the absence of evidence of renal artery stenosis, no further work-up is needed. Otherwise, an abdominal angiogram in the 20-degree LAO projection will be performed prior to device placement.;
- Current medication history including all hypertensive medication;
- Physical examination;
- NIH Stroke Scale (NIHSS); and
- Laboratory testing, including hemoglobin (Hg), platelet count (Plt), prothrombin time (PT), partial thromboplastin time (PTT), international normalized ratio (INR), high-density lipoprotein (HDL), low-density lipoprotein (LDL-C), creatinine (Cr), glucose, and pregnancy test (if subject is a female with child-bearing potential).

Local laboratories with appropriate certifications will be used for all laboratory testing.

- 12 lead electrocardiogram.

To avoid repeat testing, any of the testing listed above, performed within 90 days prior to presentation for the initial baseline assessment, may be used as baseline data.

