6.1 INCLUSION CRITERIA

Candidates for this study must meet the following criteria to be enrolled in the study, as determined in the following screening and baseline visits:

Baseline Screening Visit 1 – (Day 0 – 14) – Assessed on Day 14

1. Provided written informed consent;
2. ≥ 18 years of age and ≤ 80 years of age;
3. Office cuff SBP ≥ 160 mmHg measured per protocol instructions (Appendix VI) following at least one (1) month of maximally tolerated therapy with at least three (3) anti-hypertensive medications, of which at least one (1) must be a diuretic. Any combination medications will be counted per the active ingredient (for example, Zestoretic (Lisinopril +HCTZ) equals two (2) anti-hypertensive medications);
4. Renal artery imaging performed within the last 12 months showing no evidence of renal artery stenosis. Acceptable imaging modalities include renal duplex, magnetic resonance angiography, CT angiography, and selective or nonselective renal angiography depending on investigator site diagnostic standards. In the absence of adequate imaging testing this inclusion criteria could also be met by obtaining a renal duplex prior to enrollment or by performing nonselective renal angiography at the time of device implantation.
5. Compliant with medications (self-reported) and daily blood pressure readings – Subject must be a minimum 80% compliant with diary entries; and
6. For females (with child-bearing potential), a negative pregnancy test and the use of a medically accepted method of birth control for the duration of the trial.

Baseline Screening Visit 2 – (Day 15 – 30) - Assessed on Day 30

1. No significant obstructive vascular disease on CTA or MRA of the aortic arch and great vessels;
2. Carotid duplex studies demonstrating no obstructive carotid disease;
3. Continued adherence to hypertension medications without anticipated changes and daily blood pressure readings – Subject must be a minimum 80% compliant with diary entries;
4. Continued office cuff SBP ≥ 160 mmHg despite at least one (1) month of therapy at maximally tolerated therapy with at least three (3) anti-hypertensive medications, of which at least one (1) must be a diuretic. Any combination medications will be counted per the active ingredient (for example, Zestoretic (Lisinopril +HCTZ) equals two (2) anti-hypertensive medications).

Day of Procedure -

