8.6 BASELINE ASSESSMENT: VISIT 2 (DAY 15-30) – (+45 DAYS)

- Assessment of patient diary;
- Office cuff blood pressure (Note: Office cuff BP recordings must be performed as detailed in Appendix IV);
- Check for orthostatic blood pressure and orthostatic pulse assessments;
- Changes of medication regimen;
- Review and assessment of adverse events;
- CTA scan or MRA to assess exclusion criteria, from root of Aortic artery to intracranial vessels;
- Duplex imaging of the carotid artery;
- Assessment for carotid hypersensitivity;
- 24 hour ambulatory blood pressure measurement (24hr ABPM); and

8.7 BASELINE ASSESSMENTS VISIT 3 (DAY OF PROCEDURE) – ASSESSED ON DAY OF PROCEDURE

- Physical examination;
- Assessment of patient diary;
- Changes of medication regimen;
- Review and assessment of adverse events;
- Office cuff blood pressure (Note: Office cuff BP recordings must be performed as detailed in Appendix IV);
- Digital subtraction angiography – Inclusion/Exclusion criteria;
- Assessment of all Inclusion/Exclusion criteria; and
- Implantation of MobiusHD.

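### The 90-day reuse rule for Visit 1 tests has no exceptions, so a pregnancy result can be up to 165 days old at Visit 2 and older at implant; the rule also admits a pre-study office BP as baseline data while no BP baseline is named

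*Combined protocol and SAP*

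**What the plan says.** Section 8.5 lists the Visit 1 assessments. They include office cuff and orthostatic BP, physical examination, the NIHSS, a laboratory panel that contains the pregnancy test, and the ECG. It closes with a reuse rule, under which any test on that list "performed within 90 days prior to presentation for the initial baseline assessment, may be used as baseline data". No item is carved out.

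The timing comes from the visit headings: "8.5 BASELINE ASSESSMENT: VISIT 1 (DAY 0-14) – ASSESSED DAY 14" and "8.6 BASELINE ASSESSMENT: VISIT 2 (DAY 15-30) – (+45 DAYS" days). Section 6.1 makes "a negative pregnancy test and the use of a medically accepted method of birth control" an inclusion criterion for women who could become pregnant. In Table 7, blood testing is ticked at Visit 1 and Discharge only, and the ECG at Visit 1 only.

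For office BP, Section 6.1 asks for at least 160 mmHg systolic at Visit 1, "following at least one (1) month of maximally tolerated therapy with at least three (3) anti-hypertensive medications", and again at Visit 2. Section 8.5 ties the measurement method to Appendix IV. Office BP is also taken at Visit 3 (Section 8.7, Table 7). The synopsis names the decrease in office cuff BP as the secondary outcome. Section 13 plans descriptive summaries and does not name the baseline reading.

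**The concern.** A look-back rule that spares a subject a second lipid panel is sensible. Applied without exception, it also reaches results whose value depends on being recent.

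The pregnancy test is the clearest case. CTA or MRA follows at Visit 2, and angiography and implantation at Visit 3. A site following the plan as written could carry out all of these on a negative result that is months old and was obtained before screening began.

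The second issue concerns the BP outcome. This is a single-arm study of up to 20 subjects, so the BP result is a before-after difference and depends on which reading counts as before. The reuse rule allows a past reading to be baseline data, and Section 13 does not settle the choice. Selecting a high reading from a patient's record and comparing later readings with it would show a fall even if the device did nothing.

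**Working it through.** **Inputs from the documents.** Look-back: 90 days before presentation (Section 8.5). Visit 1: Day 0 to 14 (Section 8.5). Visit 2: Day 15 to 30, plus 45 days (Section 8.6). The plan states no maximum age for a result, so there is no figure of its own to reproduce.

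**Age of a reused result at Visit 2.** Maximum age = 90 + (Visit 2 day − presentation day). The latest Visit 2 is Day 30 + 45 = Day 75.

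| Presentation | Visit 2 on Day 15 | Day 30 | Day 75 |
|---|---|---|---|
| Day 0 | 90 + 15 = 105 | 90 + 30 = 120 | 90 + 75 = 165 |
| Day 14 | 90 + 1 = 91 | 90 + 16 = 106 | 90 + 61 = 151 |

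The worst case at Visit 2 is 165 days, if presentation is Day 0 and the 45 days run from Day 30. It is not a ceiling at implantation, because the text gives no maximum interval from Visit 2 to the procedure (the flow charts are not reproduced in the text).

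**Which Visit 1 items are repeated before the device is placed?**

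| Item | Scheduled repeat before implant |
|---|---|
| Pregnancy test | None |
| Creatinine (GFR exclusion), platelets, coagulation | None |
| ECG | None |
| Office BP | Visit 2 (threshold applied again) and Visit 3 |
| Orthostatic BP and pulse | Visit 2 |
| Physical examination | Visit 3 |
| Neurological exam | Visit 3 in Table 7; not listed in Section 8.7 |

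The age problem therefore bites on the first three rows.

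**What the choice of BP baseline is worth.** The documents give no variances, so this is a scenario calculation on assumed inputs: population mean 150 to 170 mmHg, between-subject SD 12, within-subject SD 8 to 12, no treatment effect. Subjects are kept if the Visit 1 and Visit 2 readings are both at least 160 mmHg.

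| Mean, within-subject SD | Visit 1 − follow-up | Visit 2 − follow-up | Visit 3 − follow-up |
|---|---|---|---|
| 170, 8 | 1.3 | 1.3 | 0.0 |
| 160, 8 | 2.4 | 2.4 | 0.0 |
| 150, 12 | 7.5 | 7.4 | 0.0 |

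Across the full range, a Visit 1 or Visit 2 baseline gives an apparent fall of roughly 1 to 7 mmHg with an inert device; a Visit 3 baseline gives none. The model contains no term for the age of the Visit 1 reading, so the figure measures threshold selection and would be the same if Visit 1 were measured on the day.

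**The case against.** A reader might infer that eligibility on BP can rest on a reading 165 days old. It cannot: the threshold must be met again at Visit 2 on a new reading, and BP is measured once more on the procedure day.

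A reader might also infer that a reused clinic reading escapes the Appendix IV method and the month of maximally tolerated three-drug therapy. The documents do not say so. Section 6.1 and the Section 8.5 list keep both conditions, and the reuse sentence relaxes only timing.

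A third tempting reading is that an old NIHSS would undermine the attribution of new deficits. Table 7 schedules a neurological exam at Visit 3, so a same-day comparison is planned, although Section 8.7 omits it.

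Nor can the 1 to 7 mmHg be charged to the 90-day rule, as the working shows. What the rule adds is freedom to choose among past readings, which was not modelled.

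The scope is also arguable. The sentence is meant to avoid repeat testing and follows directly on the laboratory and ECG items, so the author may have had only those in mind. The wording is nevertheless broad enough for a site to apply it to BP without deviating, and the pregnancy test falls under it on either reading.

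Finally, contraception is required throughout the trial, and Section 8.7 calls for all eligibility criteria to be assessed on the procedure day. Both mitigate the pregnancy gap. Neither schedules a test.

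**Conclusion.** The point holds for items with no scheduled repeat before implant, above all the pregnancy test: up to 165 days old at the latest Visit 2, 120 days at Day 30, and older at implantation. This rests on presentation at Day 0 and on the 45 days being added to Day 30. Creatinine, platelets, coagulation and the ECG share the exposure.

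For BP the point is narrower. A past reading that meets the method and therapy conditions may satisfy the Visit 1 criterion and serve as baseline data, and the plan does not name the baseline for its secondary outcome. If a reading used for selection were chosen, the apparent fall could be inflated by about 1 to 7 mmHg under assumed means and SDs. That is a consequence of selection and of the undefined baseline.

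Since the analysis is descriptive, no test or sample size is affected. This is an inexpensive improvement to safety and to the reading of the BP result.

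**What to change.** 1. In the Section 8.5 reuse sentence, exclude the pregnancy test and office and orthostatic BP, so that both are done within the study screening period. A pregnancy result is then at most 75 days old at the latest Visit 2 (Day 75 − Day 0) instead of 165. The sponsor should also decide whether to state a maximum interval to the procedure.
2. Have the sponsor confirm whether creatinine, platelets and coagulation should stay reusable. The ECG can be settled in the same sentence.
3. In Section 13, name the baseline for the change in office BP as a study reading not used for selection. The Visit 3 office reading is already scheduled. Report the change from Visit 2 as a sensitivity analysis, noting that Visit 2 was itself subject to the threshold.
4. Reconcile Section 8.7 with Table 7 on the Visit 3 neurological exam.

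Cost: a few sentences and one extra pregnancy test in some subjects. The apparent BP fall may also be smaller, because a selected baseline no longer contributes to it.

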8.6 BASELINE ASSESSMENT: VISIT 2 (DAY 15-30) – (+45 DAYS)

- Assessment of patient diary;
- Office cuff blood pressure (Note: Office cuff BP recordings must be performed as detailed in Appendix IV);
- Check for orthostatic blood pressure and orthostatic pulse assessments;
- Changes of medication regimen;
- Review and assessment of adverse events;
- CTA scan or MRA to assess exclusion criteria, from root of Aortic artery to intracranial vessels;
- Duplex imaging of the carotid artery;
- Assessment for carotid hypersensitivity;
- 24 hour ambulatory blood pressure measurement (24hr ABPM); and

8.7 BASELINE ASSESSMENTS VISIT 3 (DAY OF PROCEDURE) – ASSESSED ON DAY OF PROCEDURE

- Physical examination;
- Assessment of patient diary;
- Changes of medication regimen;
- Review and assessment of adverse events;
- Office cuff blood pressure (Note: Office cuff BP recordings must be performed as detailed in Appendix IV);
- Digital subtraction angiography – Inclusion/Exclusion criteria;
- Assessment of all Inclusion/Exclusion criteria; and
- Implantation of MobiusHD.

8.8 BASELINE ANGIOGRAM

After consent, all subjects should complete the baseline assessments outlined in Sections 8.5 – 8.7 and the Schedule of Study Visits and Assessments (Table 7). Subjects who meet all Inclusion/Exclusion criteria should then undergo angiogram according to imaging guidelines to measure and check the remaining Inclusion/Exclusion criteria. If renal duplex, renal MRA, renal CTA or renal angiography was performed in the 12 months preceding screening and showed no evidence of renal artery stenosis then no further work-up is needed. If no workup has been done then an abdominal angiogram in the 20 degree

LAO projection will be done prior to device implantation. During this angiogram procedure, if all Inclusion/Exclusion criteria are met, then the subject may be treated with the MobiusHD.

8.9 MOBIUSHD PROCEDURE

Prior to implantation, all assessment data should be entered into the eDC and there should be documentation that the patient has taken the dual antiplatelet regimen for the three (3) days. Also, diabetic subjects taking drugs containing metformin should be switched to insulin management the night before the implant procedure and should not be restarted on metformin until 48 hours after the last injection of contrast dye.

The patient will be placed in the standard supine position on the imaging table and prepped and draped as with any standard carotid transcatheter therapeutic or diagnostic study. Use of a head-stabilizing device is optional for this study and depends on physician preference. Light sedation and local anesthesia is recommended to allow for clinical neurological assessment, as needed.

In patients without adequate pre-procedure work-up for renal artery stenosis, non-selective renal angiography should be performed based on local technique preferences. In the absence of a local preference, begin with placement of the pigtail or lateral spray (i.e., tennis racket) catheter at the level of L-1. Make certain the catheter is easily movable and can rotate to ensure the tip is not inadvertently positioned in a thoracic or lumbar branch. Place the image intensifier at 20 degrees left anterior oblique and inject 15 cc/sec for 2 seconds under breath-hold conditions with digital subtraction. Different obliquity images may be needed if the renal ostia are eclipsed by overlying mesenteric vessels.

Heparin is given during the angiogram and implantation procedures (100 I.U./kg). ACT > 250 must be documented before implantation and measurement of platelet function is recommended according to local carotid stent protocols.

The aortic arch is defined by baseline angiography in the left anterior oblique projection. Selective carotid angiography of the target vessel for implant is performed in orthogonal views. If the aortic arch and carotid meet the study inclusion criteria then the operator will proceed with the implant.

The target common carotid is accessed with a 6 Fr kink-resistant sheath or an 8 Fr guiding catheter using the external carotid anchor-wire, telescoping technique or whatever approach the operator typically uses for carotid stenting. The guide or sheath tip should be in a stable position within the common carotid prior to removal of the .035 or .038 inch wire.

Once the guiding catheter or sheath is in position and the ACT is above 250 seconds, the ICA is accessed with a .014 inch guidewire. The implant delivery catheter is then prepared and introduced over the guidewire. Carotid imaging and roadmaps may be useful at this time. Selection of the implant size should be based on the angiographic measurements of the carotid sinus and these should coincide with the non-invasive (Duplex and or CTA) measurements. To select an appropriate implant size, select the size that correlates to the measurement made of the diameter of the carotid sinus.

Some degree of distal embolization likely occurs during all transcatheter interventional procedures. The clinical sequela is defined by the sensitivity of the target organ to segmental ischemia and the burden of embolic load.¹⁴ Due to the low burden of embolic load expected in this procedure due to the inclusion and exclusion criteria the use of a protection device is based on operator preference. Distal protection may be used with any FDA-approved distal protection device but is not mandatory. Precise placement of the implant within the sinus is required and should be controlled by road map or contrast injections. Gentle forward and backward movements may be needed as with a carotid stent, to release tension and eliminate redundancy within the delivery catheter. Implant delivery is performed by very slow retraction of the implant delivery catheter sheath and this is performed by releasing the initial lock, then sliding the control knob proximally. The device will flower open and during this maneuver movement of the delivery catheter must be strictly avoided. The operator has the opportunity to re-sheath and reposition or release the second lock and deploy the implant, depending on his or her satisfaction with the implant position and apposition. Following implantation, the delivery catheter is removed; fluoroscopic guidance should be used until the nosecone is retracted past the implant. Post procedure angiography should be performed to evaluate proper implant positioning, apposition, and maintenance of the vessel lumen. Completion angiograms should display the implanted site and the dependent territory in at least two (2) orthogonal planes.

Refer to the IFU (Appendix VI) for detailed preparation procedures and detailed sizing and placement of the device.

